8.2.2.2.2. Analysis of binary secondary endpoints

Unless otherwise stated, all primary analyses for the binary secondary endpoints are based on the FAS population with OC missing value imputation. Baseline is defined as the score for each assessment prior to the first dosing. These endpoints include:

Binary secondary endpoints include:

- *Proportion of subjects achieving the IGA for clear (0) or almost clear (1) and ≥ 2 points improvement from baseline at all scheduled time points except Week 12*
- *Proportion of subjects achieving ≥ 3 points improvement in the pruritus numerical rating scale (NRS) from baseline at all scheduled time points*
- *Proportion of subjects achieving ≥ 4 points improvement in the pruritus numerical rating scale (NRS) from baseline at all scheduled time points*
- *Proportion of subjects achieving ≥ 2 points improvement in the IGA from baseline at all scheduled time points*
- *Proportion of subjects achieving a $\geq 50\%$, 75% and 90% improvement in the EASI total score (EASI50, EASI75, EASI90) at all scheduled time points*
- *Proportion of subjects achieving a $\geq 50\%$ and 75% improvement in SCORAD (SCORAD50, SCORAD75) from baseline at all scheduled time points*

All binary secondary endpoints at each visit (except Week 12 for IGA response) will be analyzed in the same fashion as the primary endpoint using GLMM. In the case of convergence issues, logistic regression analysis at each time point with NR imputation will be performed.

For endpoint “Proportion of subjects achieving ≥ 3 points improvement in the pruritus numerical rating scale (NRS) from baseline at all scheduled time points”, subjects with baseline NRS ≤ 2 will be considered as non-responders.

For endpoint “Proportion of subjects achieving ≥ 4 points improvement in the pruritus numerical rating scale (NRS) from baseline at all scheduled time points”, only subjects with baseline NRS ≥ 4 will be analyzed.

Survival analysis will be performed for time-to-event data such as time to achieving ≥ 3 points improvement in NRS and time to achieving ≥ 4 points improvement in NRS as described in section 8.1.3.

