9.2. Efficacy Analysis

9.2.1. Analysis of the Primary Endpoint

When the 12 week treatment period is completed, the analysis of the primary endpoint will be conducted. The primary endpoint is the proportion of IGA responders at Week 12 and the corresponding primary analysis will be based on the normal approximation for the difference in binomial proportions (such as IGA response rates) to test the superiority of each dose of PF-04965842 to placebo at Week 12. Subjects who receive at least one investigational product and discontinue from the study before Week 12 will be considered as non-responders for the primary endpoint (IGA) for all subsequent visits during the treatment phase until Week 12. Bayesian analysis using a non-informative prior (such as Jeffery's prior) may be employed if the normality assumption does not hold.

Sensitivity analysis will be performed with a generalized linear mixed model utilizing the data from all scheduled visits if there is no convergence issue. This model will have fixed effects for time, treatment, time by treatment interaction and other potential covariates. The dependent variable will be logit of the probability of “response”. An unstructured correlation may be used to model the association between observations within a subject. The modified intention-to-treat (mITT) population will be the subjects who receive at least one dose of randomized investigational product (PF-04965842 or placebo). In addition, dose-response analysis using an Emax model may be provided for the primary endpoint.

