The binary secondary endpoints such as proportion of subjects achieving the IGA for clear (0) or almost clear (1) and ≥ 2 points improvement from baseline at all scheduled time points except Week 12, proportion of subjects with the IGA response of ≥ 2 points improvement from baseline at all scheduled time points, proportions of subjects achieving 50%, 75% and 90% reduction in EASI total score from baseline at all scheduled time points, proportion of subjects with improvement (reduction) of the pruritus NRS ≥ 3 from baseline at all scheduled time points and Proportion of subjects achieving a 50% and 75% improvement in SCORAD (SCORAD50, SCORAD75) from baseline at all scheduled time points will be analyzed using the same method specified for the primary endpoint in [Section 9.2.1](#). We will calculate estimate and 90% confidence interval for the difference of proportions (each of the active doses against placebo) using normal approximation to the distribution of the observed difference in proportions.

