7.1. Efficacy Data

[figure not shown]
For the binary efficacy data such as IGA response, subjects who receive at least one investigational product and discontinue from the study before Week 12 will be considered as non-responders (NR) for all subsequent visits during the treatment phase until Week 12.

For the continuous efficacy endpoints such as percent change from baseline in EASI score at Week 12, the observed case (OC) approach and the last efficacy observation carrying forward (LOCF) missing value imputation will both be considered. The efficacy endpoints will be set to missing after rescue treatment is used. The LOCF method will then be used to impute missing values.

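### SAP 7.1 makes dropouts non-responders for binary efficacy data, but the binary secondary endpoints are analysed on observed cases and revert to non-responder imputation only when the model does not converge

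*SAP*

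**What the plan says.** **General rule.** SAP 7.1 covers the binary efficacy data as a class, naming IGA response as an example. Treated subjects whose participation ends before the Week 12 visit "will be considered as non-responders (NR) for all subsequent visits during the treatment phase until Week 12". The section offers observed cases (OC) and LOCF only for continuous endpoints.

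**Binary secondary endpoints.** SAP 8.2.2.2.2 states that "all primary analyses for the binary secondary endpoints are based on the FAS population with OC missing value imputation", using a generalised linear mixed model (GLMM). SAP 8.1.1.2 says the same for other binary endpoints. Table 8.2.5 labels GLMM with OC as the primary approach for NRS improvement of at least 3 and at least 4 points, IGA improvement of at least 2 points, EASI50/75/90 and SCORAD50/75. SAP 8.2.2.4 applies OC and GLMM to PtGA response, which has no row in table 8.2.5.

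**Fallback.** SAP 8.2.2.2.2: "In the case of convergence issues, logistic regression analysis at each time point with NR imputation will be performed". SAP 8.2.2.4 has the same switch for PtGA response. SAP 8.1.1.2 makes it optional (*may*), where 8.2.2.2.2 makes it firm (*will*).

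**IGA response away from Week 12.** SAP 8.2.2.2.2 lists it among the endpoints analysed by GLMM with OC. Table 8.2.5 gives Emax with NR as the primary approach for IGA response in its combined primary/secondary row.

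**Protocol.** Section 9.2.2 says that the binary secondary endpoints "will be analyzed using the same method specified for the primary endpoint in" Section 9.2.1.

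**The concern.** A programmer cannot follow both 7.1 and 8.2.2.2.2. Under 7.1 a subject who leaves at Week 4 is a non-responder for EASI75 at Week 12. Under 8.2.2.2.2 the same subject has no Week 12 outcome, and the model relies on missingness at random.

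The fallback makes this worse. A convergence fallback should change the computation and leave the estimand alone. Here it changes how dropout is treated, endpoint by endpoint, according to whether a fit converges. Two neighbouring endpoints could then be reported under different rules for no scientific reason.

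Dropout may well be related to treatment. Protocol Appendix 11.2 requires discontinuation for confirmed laboratory abnormalities and for serious infections, and Protocol 1.8.2 reports platelet reductions in all active groups of the earlier psoriasis study. Protocol 5.8.2 stops other treatments that could affect the disease, except oral antihistamines, so leaving for lack of effect is also plausible. The first would raise dropout on active drug and the second on placebo. The two rules respond differently to each.

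**Working it through.** **1. The plan's own figure.** SAP 4.2.4 gives about 95% power for 43% against 10% at 0.0125. SAP 4.2.2 sets 0.05 one-sided, and 0.05/4 = 0.0125. With 50 randomised per arm and pooled variance under the null, the mean rate is 0.265 and z(0.9875) = 2.2414:

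- null SE = √(2 × 0.265 × 0.735 / 50) = 0.0883
- alternative SE = √((0.10 × 0.90 + 0.43 × 0.57) / 50) = 0.0819
- power = Φ((0.33 − 2.2414 × 0.0883) / 0.0819) = 94.7%

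The figure reproduces on 50 per arm; on 40 completers per arm the same formula gives 88.3%. The present point does not rest on it. It does show that the plan does not settle whether 43% and 10% are rates among completers or among all randomised, so step 3 has to assume one.

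**2. Rule by endpoint.**

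| Endpoint | Primary rule | If GLMM fails | NR output regardless of convergence |
|---|---|---|---|
| IGA response, Week 12 | Emax, NR (8.1.1.1, 8.2.2.1) | not applicable | yes: logistic regression |
| IGA response, other visits | OC GLMM (8.2.2.2.2) or Emax NR (8.2.5) | NR logistic | yes: per-visit logistic regression (8.2.2.1) |
| EASI50/75/90, NRS response | OC GLMM | NR logistic | tables and figures only (8.1.1) |
| SCORAD50/75 | OC GLMM | NR logistic | none |
| IGA improvement of at least 2 points | OC GLMM | NR logistic | none |
| PtGA response | OC GLMM (8.2.2.4) | NR logistic | none |

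IGA improvement of at least 2 points has its own line because SAP Appendix 2 defines IGA response as a score of 0 or 1 together with that improvement. The NR tables named in 8.1.1 therefore do not cover it.

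**3. Size, at a single visit.** Inputs: 43% and 10% are the Week 12 IGA planning rates, taken here as rates among observed subjects and used only as an example, because the documents give no rate for an affected endpoint. The 20% dropout is from SAP 4.2.4; the 10%/30% splits are assumptions that keep the two-arm average at 20%.

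- OC difference = pA − pP = 0.43 − 0.10 = 0.330
- NR difference = pA(1 − dA) − pP(1 − dP)

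| Dropout active / placebo | NR active | NR placebo | NR difference | Gap from OC |
|---|---|---|---|---|
| 20% / 20% | 0.43 × 0.8 = 0.344 | 0.10 × 0.8 = 0.080 | 0.264 | 6.6 points |
| 10% / 30% | 0.43 × 0.9 = 0.387 | 0.10 × 0.7 = 0.070 | 0.317 | 1.3 points |
| 30% / 10% | 0.43 × 0.7 = 0.301 | 0.10 × 0.9 = 0.090 | 0.211 | 11.9 points |

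NR can also create a difference. If 30% of observed subjects respond in both arms, OC shows none, but 10% active and 30% placebo dropout gives 0.30 × 0.9 − 0.30 × 0.7 = 0.06 under NR.

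**The case against.** **The observed-case analysis is not a completers analysis.** A reader might infer that dropouts are simply removed. The documents do not support that. SAP 8.1.1.1 specifies a longitudinal model with a subject-level random intercept and a treatment-by-visit term, so a dropout's earlier visits still contribute under missing at random. This stands: the gaps above are for raw proportions, and the model-based gap may differ. The GLMM still does not count discontinuation as failure, which is what 7.1 requires.

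**The protocol does not plainly require NR for these endpoints.** It is tempting to say that the SAP breaches Protocol 9.2.2. That section reaches NR only by pointing to 9.2.1, where the non-responder sentence names the primary endpoint. Protocol section 9 also lets the SAP modify the plan, with major changes made before unblinding going into an amendment. The firm conflict is therefore inside the SAP.

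**Some NR results are already planned.** This is true for IGA response at every visit, and descriptively for EASI50/75/90 and NRS response. It leaves SCORAD50/75, IGA improvement of at least 2 points and PtGA response with nothing, and it does not settle which rule is primary.

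**Qualifying words.** SAP 8.2.2.2.2 opens with an exception for anything stated otherwise, which might be read as deferring to 7.1. Table 8.2.5 closes that route by labelling OC as primary. For PtGA response the objection has more force, because SAP 7.3 separately allows OC for some patient-reported analyses.

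**NR is a choice.** The contradiction shows that one rule is needed, without dictating which, and NR has its own weakness under unequal dropout. This stands.

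**Conclusion.** The SAP gives two incompatible missing-data rules for the binary secondary endpoints, and its convergence fallback moves from one to the other. For IGA response away from Week 12 it also names two primary approaches. These faults are in the current text.

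The size is uncertain. On the single-visit illustration the rules differ by about 1 to 12 points on a 33-point difference, depending on which arm loses more subjects. That rests on borrowed Week 12 IGA planning rates, read as rates among observed subjects, and on assumed dropout splits around the plan's 20%.

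A reader might infer that the trial's main conclusion is at risk. It is not: Week 12 IGA response is analysed with NR, and SAP 4.1 and 4.2.2 confine formal inference and multiplicity control to that endpoint. What is at stake is the interpretability and consistency of the secondary results. The correction is worth making before unblinding, though it does not threaten the primary analysis.

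**What to change.** - State one primary missing-data rule through Week 12, identically in SAP 7.1, 8.1.1.2, 8.2.2.2.2, 8.2.2.4 and 8.2.5. NR is the natural candidate: 7.1 already states it and the primary endpoint uses it.
- Keep that rule in any convergence fallback, so that only the model or the fitting method changes. Align *may* in 8.1.1.2 with *will* in 8.2.2.2.2.
- Run the OC GLMM as a sensitivity analysis for every binary secondary endpoint, whether or not a fallback is needed elsewhere.
- In 8.2.5, separate IGA response at Week 12 from the other visits, give each one primary approach, and add a row for PtGA response.
- Reconcile PtGA response with 7.3.
- State the handling of follow-up visits separately, since the 7.1 rule ends at Week 12 while 8.2.5 includes follow-up.

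**Cost.** SAP wording, plus per-visit NR logistic regressions for endpoints where they now exist only as a fallback: NRS response, EASI50/75/90, SCORAD50/75, IGA improvement of at least 2 points and PtGA response. The method is specified in 8.1.1.1, but the example code in Appendices 11 and 12 covers only the GLMM and Emax models. Reported response rates would be lower than on observed cases; in the equal-dropout illustration 43% becomes 34.4%. No new data are needed.

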8.2.2.3. CCI [REDACTED]

CCI [REDACTED] IP-

8.2.2.4. Analyses for the Patient-Reported Outcome (PRO) Endpoints

Unless otherwise stated, all primary analyses for the PRO endpoints are based on the FAS population with OC missing value imputation. Baseline is defined as the score for each assessment prior to the first dosing.

[figure not shown]
PRO endpoints include:

- *Change from baseline in pruritus NRS score at all scheduled time points*
- *Proportion of subjects with patient global assessment (PtGA) of AD of clear (0) or almost clear (1) and ≥ 2 points improvement from baseline at all scheduled time points*
- *Change from baseline in dermatology life quality index (DLQI) total score at all scheduled time points*
- *Change from baseline in patient Oriented Eczema Measure (POEM) at all scheduled time points*
- *Change from baseline in the hospital and anxiety depression scale (HADS) at all scheduled time points*

The binary PRO endpoint such as PtGA response will be analyzed in the same fashion as the primary endpoint using GLMM as described in Section 8.1.1.1. In the case of convergence issues, logistic regression analysis at each time point will be performed with NR imputation. All continuous PRO endpoints will be analyzed using MMRM as described in Section 8.1.2. LS means at each time point will be computed. P values and 90% confidence intervals will also be computed for placebo adjusted effect (LS mean difference between treatment and placebo) at each time point. In case of convergence issues, ANCOVA with LOCF may be performed at each time point.

ePRO data on the CCI [REDACTED] will be assessed psychometrically as stated in a separate SAP. Summary statistics will be generated as described in section 8.2.2.3.

090177e18dabc776\0.1\Draft\Versioned On:07-Feb-2018 10:11 (GMT)

The overall CCI score will be calculated as the mean of the 11 items representing CCI scale as shown in Appendix 14.

8.2.3. Statistical Analyses for Safety

The analysis population for safety is described in Section 5.2. Safety and tolerability will be assessed by clinical review of all relevant parameters including adverse experiences (AEs) and laboratory tests. A complete list of laboratory parameters can be obtained in Section 7.3 of the protocol.

All the tables, listings and graphs for adverse events, lab parameters and vital sign will follow Pfizer standards.

A 3-tier approach will be used to summarize AEs. Under this approach, AEs are classified into 1 of 3 tiers.

Tier-1 events: These are pre-specified events of clinical importance and are maintained in a list in the product's Safety Review Plan.

Tier-2 events: These are events that are not tier-1 but are "common". A MedDRA Preferred Term (PT) is defined as a tier-2 event if there are at least 4 in any treatment group.

Tier-3 events: These are events that are neither tier-1 nor tier-2 events.

There will be no adjustment for multiple comparisons or stratification factors in the analyses unless specified. For tier-1 and tier-2 events, the proportion of AEs observed in each treatment groups will be presented along with the point estimates and associated 90% confidence intervals of the risk difference for each active treatment compared with placebo. The exact methods (Chan and Zhang, 1999) and asymptotic approach will be employed for analysis of tier-1 and tier-2 events. For tier-1 events p-values may be included in the presentations. AEs will be arranged in the output sorted in descending point estimate of the risk difference within system organ class. Footnotes in the outputs will include the methods used to derive any p-values and confidence intervals as per Pfizer standards. The exposure adjusted summaries for the Tier 1 and Tier 2 events will also be conducted.

8.2.4. PK and PK/PD Analyses

PK concentrations will be summarized and presented by treatment group with summary statistics and, where appropriate, non-compartmental PK parameters estimates will be provided. A population PK model may be developed for the purpose of estimating PK parameters. Population PK data for PF-04965842 will be summarized through appropriate data tabulations, descriptive statistics, and graphical presentation. Data permitting, the relationship between exposure and clinical responses (efficacy and safety) and disease and mechanism related PD biomarkers during treatment of subjects with moderate to severe AD may be explored using either observed or modeled exposures. Any population analyses conducted will not be part of the clinical study report and may be reported separately.

The PK/PD analysis plan will be detailed in another document.

8.2.5. Brief Summary of Major Efficacy, Health Outcome and Biomarker Analyses

Endpoints	Primary, Secondary, or Exploratory Endpoint	Analysis	Including Follow-UP	Missing Data Imputation	Primary or Sensitivity Approach
IGA Response	Primary/Secondary	E _{max}	Yes	NR	Primary
IGA Response	Primary/Secondary	GLMM	Yes	OC	Sensitivity
IGA Response	Primary/Secondary	Logistic regression	Yes	NR	Sensitivity
Percent change of EASI	Secondary	MMRM	Yes	OC	Primary
Change of EASI	Secondary	MMRM	Yes	OC	Sensitivity
Percent change of NRS	Secondary	MMRM	Yes	OC	Primary
Change of BSA	Secondary	MMRM	Yes	OC	Primary
Change of SCORAD	Secondary	MMRM	Yes	OC	Primary
Percent change of SCORAD	Secondary	MMRM	Yes	OC	Primary
Proportion of subjects achieving ≥ 3 NRS improvement	Secondary	GLMM	Yes	OC	Primary
Proportion of subjects achieving ≥ 4 NRS improvement	New endpoint	GLMM	Yes	OC	Primary
Proportion of subjects achieving ≥ 2 IGA improvement	Secondary	GLMM	Yes	OC	Primary
EASI50/EASI75/EASI90	Secondary	GLMM	Yes	OC	Primary
SCORAD50/SCORAD75	Secondary	GLMM	Yes	OC	Primary
Change of NRS	PRO	MMRM	Yes	OC	Primary
Change of DLQI	PRO	MMRM	Yes	OC	Primary
Change of POEM	PRO	MMRM	Yes	OC	Primary
Change of HADS	PRO	MMRM	Yes	OC	Primary

090177e18dabc776\0.1\Draft\Versioned On:07-Feb-2018 10:11 (GMT)

10. APPENDICES

Appendix 1. DEFINITION AND USE OF VISIT WINDOWS IN REPORTING

Note Day 1 in the table below is taken as the first day of dosing with study drug. It may not be the same as the first study date which is the randomization date. Also note that Day 0 does not exist, so Day -1 is the day before Day 1. Also the relative days (rel_day) from Day 1 are defined as the visit date minus first dosing date plus one.

Visit windows will be used for efficacy variables, and for any safety displays that display by week.

Table 1. Visit Window Definition for Analysis (update wider visit windows)

Visit No.	Visit Label	Target Day	Visit Window
1	Screening	N/A	-35≤rel_day≤-1
2	Baseline*	1	Rel_day= 1
3	Week 1	8	2≤rel_day≤11
4	Week 2	15	12≤rel_day≤22
5	Week 4	29	23≤rel_day≤36
6	Week 6	43	37≤rel_day≤50
7	Week 8	57	51≤rel_day≤71
8	Week 12	85	72≤rel_day≤88
9	Week 13	92	89≤rel_day≤95
10	Week 14	99	96≤rel_day≤106
11	Week 16	113	107≤rel_day≤120

* Baseline analysis visit window may be considered as Rel_day≤1 in some analyses (eg, those involving change from baseline). That is, in case that Day 1 observation is missing, the last observation by the first dosing date may be considered as the baseline.

090177e18dabc776\0.1\Draft\Versioned On:07-Feb-2018 10:11 (GMT)

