6.2.7. Visit 8, Day 85/Week 12 (± 3 day)

- Conduct complete physical examination.
- Obtain vital signs including pulse rate, blood pressure, respiratory rate (after at least 5 minutes of rest) and oral or tympanic temperature.
- Obtain **fasting** samples for blood chemistry including lipid profile.
- Obtain samples for laboratory testing: hematology, urinalysis, urine pregnancy test (female subjects of childbearing potential only), EBV, CMV, HSV1, HSV2, VZV, IgE, hsCRP, IP-10, IL-31, CCL17, TBNK, T cell subsets, and exploratory biomarker samples.
- **Prior to dosing**, obtain samples for PK analysis (the first PK sample is to be collected 2 hours (± 30 minutes) prior to dosing; the second PK sample is to be collected immediately prior to dosing).
- Photography at selected sites (at PI's discretion).
- Conduct clinical evaluations including IGA, EASI, BSA, and SCORAD.
- Administer PROs including Pruritus NRS, PtGA, DLQI, POEM, and HADS.
- Review **CCI** (in selected country/ies) as necessary.
- Perform single 12-lead ECG.

- Confirm proper contraception is being used.
- Review any changes in the subject's concomitant treatments information.
- Perform drug accountability procedures.
- Administer study drug to the subject.
- Obtain samples for PK analysis at 1 hour (± 30 minutes), 2 hour (± 30 minutes), and 4 hour (± 30 minutes), after dosing.
- Assess for occurrence of Adverse Events by spontaneous reporting of adverse events and by asking the subjects to respond to a non-leading question such as "How do you feel?"

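### A Week 12 visit held after Day 88 with the subject still on study drug is filed as follow-up, and the primary endpoint is then most likely scored as non-response whatever IGA was recorded

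*SAP*

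**What the plan says.** SAP Appendix 1 states that "Visit windows will be used for efficacy variables, and for any safety displays that display by week". The relative day is "defined as the visit date minus first dosing date plus one". Table 1 gives Week 12 as "72≤rel_day≤88", Week 13 as "89≤rel_day≤95" and Week 14 as "96≤rel_day≤106". It does not say that the nominal visit number ever overrides the day count, and it has no rule for two assessments falling in one window.

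Protocol Section 6.2.7 places Visit 8 at Day 85, plus or minus 3 days. That visit includes IGA and EASI and the instruction "Administer study drug to the subject". Protocol Sections 6.3.1 and 6.3.2 put Weeks 13 and 14 in follow-up. Note n to the Schedule of Activities has dosing run from Day 1 to Day 85.

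On missing binary data, SAP Section 7.1 applies non-responder (NR) scoring to treated subjects who "discontinue from the study before Week 12 will be considered as non-responders (NR) for all subsequent visits" up to Week 12. Section 8.1.1.1 says NR handles missing values in the primary analysis and refers back to 7.1. Section 8.2.2.1 names NR as the imputation method for the primary endpoint without that restriction, and the summary table in 8.2.5 lists NR for the Emax analysis.

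**The concern.** Visit 8 is the end-of-treatment visit and supplies the primary endpoint. If it slips past Day 88, the assessments are still made, but the day count moves them to a follow-up week. The subject did not discontinue and has a recorded IGA, yet has no observed Week 12 value.

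Three things follow.

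- A responder seen late is probably counted as a failure in the primary Emax analysis.
- In the observed-case MMRM and GLMM, which include follow-up, an end-of-treatment score leaves the Week 12 estimate and enters a follow-up estimate.
- Two assessments can land in one window. Visit 8 on Day 90 and Visit 9 on Day 94 would both be Week 13, with no rule for choosing between them.

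Late visits are foreseeable at about 60 sites, and how to treat them should not be settled once treatment codes are known.

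**Working it through.** **1. Reproduce the window limits.** Inputs are the target days in SAP Table 1. Rule tested: upper limit = midpoint of adjacent targets, rounded down.

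| Window | Midpoint with next target | Printed upper limit |
|---|---|---|
| Week 1 | (8+15)/2 = 11.5 | 11 |
| Week 2 | (15+29)/2 = 22 | 22 |
| Week 4 | (29+43)/2 = 36 | 36 |
| Week 6 | (43+57)/2 = 50 | 50 |
| Week 8 | (57+85)/2 = 71 | 71 |
| Week 12 | (85+92)/2 = 88.5 | 88 |
| Week 13 | (92+99)/2 = 95.5 | 95 |
| Week 14 | (99+113)/2 = 106 | 106 |

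All eight boundaries follow the rule, with no gaps or overlaps.

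**2. Compare with the protocol window.** For Visit 8, 85 - 3 = 82 and 85 + 3 = 88. The analysis window therefore contains every permitted Visit 8 date. It extends 85 - 72 = 13 days before target and 88 - 85 = 3 days after. Late allowance beyond the protocol limit:

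- Week 1: 11 - 9 = 2 days
- Weeks 2, 4 and 6: 6 days each (22 - 16, 36 - 30, 50 - 44)
- Week 8: 71 - 60 = 11 days
- Week 12: 88 - 88 = 0 days
- Week 13: 95 - 95 = 0 days

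**3. Map a late Visit 8.** Days 86-88 map to Week 12, Days 89-95 to Week 13 and Days 96-106 to Week 14.

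**4. Score the resulting gap.** Section 7.1 requires discontinuation before Week 12, which a completer does not meet. Section 8.2.2.1 and the table in 8.2.5 apply NR to the primary endpoint generally. Section 8.1.1.1 does too, but by reference to 7.1. NR is the likelier outcome; read strictly, 7.1 assigns no value.

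**5. Size, under a stated assumption.** The documents give no rate of late visits. Assume a share f in every arm, unrelated to response, all scored NR. SAP Section 4.2.4 gives 10% on placebo and a 33-point difference, hence 43% on active drug. The 250 randomized make 50 per arm. Each rate is multiplied by (1 - f).

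- f = 2%: 1 subject per arm (5 of 250). 43 x 0.98 = 42.1; 10 x 0.98 = 9.8; difference 33 x 0.98 = 32.3 points.
- f = 5%: 2.5 per arm (12.5 of 250). 43 x 0.95 = 40.9; 10 x 0.95 = 9.5; difference 33 x 0.95 = 31.4 points.

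**6. Power.** Power = Phi{[d - z x sqrt(2 x pbar x (1 - pbar)/n)] / sqrt[(p0(1 - p0) + p1(1 - p1))/n]}, where d = p1 - p0 and pbar is the mean of the two rates. Take n = 50 and one-sided 0.0125 (z = 2.241). This setting comes close to the plan's 95%, though the plan does not state sidedness.

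- No late visits: (0.33 - 2.241 x 0.0883)/0.0819 = 1.61, power 94.7%.
- f = 2%: 94.0%.
- f = 5%: (0.3135 - 2.241 x 0.0868)/0.0809 = 1.47, power 92.9%.

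If the same subjects were dropped instead, power would be 94.2% and 93.5%.

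**The case against.** The strongest reply is that the window is correct as built, and it is. Day 88 follows the same midpoint rule as every other boundary and matches the protocol tolerance. A reader might see the 13-day early and 3-day late sides as a mistake special to the primary time point, but they arise because the preceding visit is 28 days earlier and the next 7 days later. Week 13 likewise has no late allowance. The note in the table's title about wider windows does not alter the printed limits.

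A reader might also infer that a late completer has no primary-endpoint value and leaves the Emax fit. Only the narrow wording of 7.1 supports that; Sections 8.1.1.1, 8.2.2.1 and 8.2.5 point to non-response. Nor does carrying Week 8 forward displace the main EASI result: the primary EASI analysis is MMRM on observed cases, and ANCOVA with LOCF is a sensitivity analysis.

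The objection with most weight concerns the remedy. Planned dosing ends on Day 85, the documents do not say how dosing runs when Visit 8 is late, and Protocol Section 1.5 gives a half-life of 2.8 to 5.0 hours after repeated dosing. Simply extending Week 12 to Day 95 could bring off-drug scores into the on-treatment time point. This stands, so the remapping must depend on recorded dosing.

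Finally, equal NR scoring in all arms shrinks the difference, which is conservative for a superiority claim. That limits the harm, but it does not justify overriding an observed response.

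**Conclusion.** The point holds in a limited form. The rule discards an observed end-of-treatment value only when Visit 8 is already outside the protocol window, the subject is still on study drug, and no other assessment falls on Days 72-88. The likely consequence is non-response regardless of the recorded IGA, and 7.1 and the Section 8 text need to agree on this.

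Under the assumed 2%-5%, the cost is 0.7 to 1.6 or 1.7 points of the 33-point difference (33 - 32.34 = 0.66; 33 - 31.35 = 1.65) and 94.7 - 94.0 = 0.7 to 94.7 - 92.9 = 1.8 points of power. These figures assume equal late rates across arms, independence from response, and that every late subject was still on drug. They do not suggest the trial's conclusion is at risk. The case for acting is that the rule is cheap to settle in advance and open to dispute afterwards.

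**What to change.** Before unblinding, amend the SAP in two places.

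- **Appendix 1:** when the attended Visit 8 falls after Day 88, assign its assessments to Week 12, provided the recorded dosing dates show the subject was on study drug up to that visit. State which recorded dates satisfy this. Start that subject's follow-up windows after the visit. Keep Days 72-88 for everyone else.
- **Section 7.1:** state that a completer with no Week 12 value after this mapping is scored NR, so that 7.1 agrees with 8.1.1.1, 8.2.2.1 and 8.2.5.

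The cost is a short SAP amendment and one programming rule. A few Week 12 values will come from several days after target, and those subjects need their own start to the Week 13 window, a small departure from fixed-day windows. If unblinding has already taken place, Protocol Section 9 requires such a change to be documented and explained in the study report.
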